9.2 Safety Event Reporting Procedures

9.2.1 Reporting Procedures for Disease-related Events

The investigator is responsible for ensuring that all Disease-Related Events observed by the investigator or reported by the subject that occur after the first dose of blinatumomab through the safety follow-up visit are recorded on the Event CRF as a Disease-Related Event.

Disease-Related Events assessed by the investigator to be more severe than expected and/or related to the investigational medicinal product(s)/study treatment/protocol-required therapies, and determined to be serious, must be recorded on the Event CRF as Serious Adverse Events.

Additionally, the investigator is required to report a fatal Disease-Related Event on the Event CRF as a Disease-Related Event.

9.2.2 Adverse Events

9.2.2.1 Reporting Procedures for Adverse Events That do not Meet Serious Criteria

The investigator is responsible for ensuring that all adverse events observed by the investigator or reported by the subject that occur after first dose of blinatumomab through the safety follow-up visit are reported using the Event CRF.

The investigator must assign the following adverse event attributes:

- adverse event diagnosis or syndrome(s), if known (if not known, signs or symptoms)
- dates of onset and resolution (if resolved)
- severity (and/or toxicity per protocol)
- assessment of relatedness to investigational product(s), medical device(s) or other protocol-required therapies
- action taken.

The adverse event grading scale used will be the Common Terminology Criteria for Adverse Events (CTCAE) version 4.0. The grading scale used in this study is described in [Appendix A](#).

The investigator must assess whether the adverse event is possibly related to the investigational product(s), and/or other protocol-required therapies. This relationship is indicated by a “yes” or “no” response to the question: Is there a reasonable possibility that the event may have been caused by the investigational product(s), and/or other protocol-required therapies?

The investigator is responsible for reviewing laboratory test results and determining whether an abnormal value in an individual study subject represents a clinically significant change from the subject's baseline values. All grade 3 and grade 4 laboratory values should be recorded as adverse events. In addition, if signs or symptoms are associated with the laboratory abnormality, the signs/symptoms and the laboratory abnormality should all be recorded as adverse events. The laboratory abnormality and any signs/symptoms should be graded according to their own CTCAE criteria.

The investigator is expected to follow reported adverse events until stabilization or reversibility.

9.2.2.2 Reporting Procedures for Serious Adverse Events

The investigator is responsible for ensuring that all serious adverse events observed by the investigator or reported by the subject that occur after signing of the informed consent through 30 days after the last dose of investigational product are recorded in the subject's medical record and are submitted to Amgen. Additionally blinatumomab-related serious adverse events that occur after the safety follow-up visit through the end of the long-term follow-up will be reported.

All serious adverse events must be submitted to Amgen within 24 hours following the investigator's knowledge of the event via the Event CRF.

If the electronic data capture (EDC) system is unavailable to the site staff to report the serious adverse event, the information is to be reported to Amgen via an electronic Serious Adverse Event Contingency Report Form within 24 hours of the investigator's knowledge of the event. See [Appendix B](#) for a sample of the Serious Adverse Event Worksheet /electronic Serious Adverse Event Contingency Report Form. For EDC studies where the first notification of a Serious Adverse Event is reported to Amgen via the eSerious Adverse Event Contingency Report Form, the data must be entered into the EDC system when the system is again available.

The investigator must assess whether the serious adverse event is possibly related to investigational product, medical device, and/or other protocol-required therapies. This relationship is indicated by a "yes" or "no" response to the question: Is there a reasonable possibility that the event may have been caused by the investigational product, medical device, and/or other protocol-required therapies? Relatedness means that there are facts or reasons to support a relationship between investigational product and the event.

The investigator is expected to follow reported serious adverse events until stabilization or reversibility.

New information relating to a previously reported serious adverse event must be submitted to Amgen. All new information for serious adverse events must be sent to Amgen within 24 hours following knowledge of the new information. If specifically requested, the investigator may need to provide additional follow-up information, such as discharge summaries, medical records, or extracts from the medical records.

Information provided about the serious adverse event must be consistent with that recorded on the Event CRF.

If a subject is permanently withdrawn from protocol-required therapies because of a serious adverse event, this information must be submitted to Amgen.

The investigator is to notify the appropriate IRB/IEC of serious adverse events occurring at the site and other adverse event reports received from Amgen, in accordance with local regulatory requirements and procedures.

9.2.2.3 Reporting Serious Adverse Events After the Protocol-required Reporting Period

There is no requirement to monitor study subjects for serious adverse events following the protocol-required reporting period or after end of study. However, these serious adverse events can be reported to Amgen. In some countries (eg, European Union [EU] member states), investigators are required to report serious adverse events that they become aware of after end of study. If serious adverse events are reported, the investigator is to report them to Amgen within 24 hours following the investigator's knowledge of the event.

Serious adverse events reported outside of the protocol-required reporting period will be captured within the safety database as clinical trial cases for the purposes of expedited reporting.

9.2.2.4 Serious Adverse Events That are not to be Reported by the Sponsors to Regulatory Agencies in an Expedited Manner

Events which are morbidities associated in general with lymphoma and lymphoma therapy do not require expedited reporting:

- Planned hospitalization

Expected disease related serious adverse events are not subjected to report individually in an expedited manner by Amgen unless it meets the criteria listed in [Section 9.1.3](#). A local Safety Review Committee will be used to monitor the benefit/risk of such events.

9.3 Pregnancy and Lactation Reporting

If a female subject becomes pregnant, or a male subject fathers a child, while the subject is taking blinatumomab report the pregnancy to Amgen Global Patient Safety as specified below.

In addition to reporting any pregnancies occurring during the study, investigators should report pregnancies that occur 48 hours after the last dose of blinatumomab.

The pregnancy should be reported to Amgen Global Patient Safety within 24 hours of the investigator's knowledge of the event of a pregnancy. Report a pregnancy on the Pregnancy Notification Worksheet ([Appendix C](#)). Amgen Global Patient Safety will follow-up with the investigator regarding additional information that may be requested.

If a female subject becomes pregnant during the study, the investigator should attempt to obtain information regarding the birth outcome and health of the infant.

If the outcome of the pregnancy meets a criterion for immediate classification as a Serious Adverse Event (eg, female subject experiences a spontaneous abortion, stillbirth, or neonatal death or there is a fetal or neonatal congenital anomaly) the investigator will report the event as a Serious Adverse Event.

If a female breastfeeds while taking protocol-required therapies report the lactation case to Amgen as specified below.

Any lactation case should be reported to Amgen Global Patient Safety within 24 hours of the investigator's knowledge of event. Report a lactation case on the Lactation Notification Worksheet ([Appendix C](#)). Amgen Global Patient Safety will follow-up with the investigator regarding additional information that may be requested.

If a male subject's female partner becomes pregnant, the investigator should discuss obtaining information regarding the birth outcome and health of the infant from the pregnant partner.

10. STATISTICAL CONSIDERATIONS

10.1 Study Endpoints, Analysis Sets, and Covariates

10.1.1 Study Endpoints

10.1.1.1 Primary Endpoint

MRD-negative rate at the end of cycle 1 of blinatumomab

10.1.1.2 Secondary Endpoint(s)

- PFS
- Duration of MRD-negative status
- OS
- Incidence, grade and severity of treatment emergent adverse events

10.1.1.3 Exploratory Endpoint(s)

- Anti-blinatumomab antibody formation
- MRD-negative rate calculated at each timepoint measured following blinatumomab treatment
- Incidence of alloHSCT (number of subjects with alloHSCT), including the methodology and clinical outcomes
- Relationship between pre-specified co-variates with MRD-negative status and clinical outcomes
- Summary of MRD characteristics prior to treatment with blinatumomab:
 - The percentage of MRD positivity in PET-CT negative subjects post aHSCT
 - Rate and timing of MRD-negative to MRD-positive change during the 24-month run-in period

10.1.2 Analysis Sets

10.1.2.1 Full Analysis Set

The full analysis set will include all subjects who received blinatumomab. Subjects who were treated beyond the required sample size of 30 subjects will be included in this analysis set. The full analysis set will be used for the final analysis.

10.1.2.2 Primary Analysis Set

The primary analysis set will include the first 30 subjects who received blinatumomab. The primary analysis set will be used for the primary analysis.

10.1.2.3 Target Dose Analysis Set

The target dose analysis set will include all subjects from the full analysis set who completed at least 7 days of infusion on the highest intended dose. In addition, all subjects who discontinue treatment with blinatumomab due to disease progression during cycle 1 will also be included in the target analysis set. The target dose analysis set will be used as sensitivity analysis set for the final analysis.

10.1.2.4 Pre-treatment Analysis Set

The pre-treatment analysis set will include all subjects that enroll in the study.

10.1.2.5 DLT Analysis Set

A subject needs to meet 1 of the following criteria to be DLT evaluable:

- The subject experiences a DLT in the DLT evaluation period; OR
- The subject is removed from treatment for an adverse event/toxicity; OR
- The subject is removed from treatment for reasons other than an adverse event/toxicity, ie, disease progression, and the subject has received at least 7 days of the target blinatumomab dose; OR
- The subject does not experience a DLT and completes DLT evaluation period.

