6.2.2 Study Stopping Rules

The DLT evaluation period will be the entire duration of cycle 1 of blinatumomab treatment. For subjects who are removed from study treatment for reasons other than an adverse event/toxicity, ie, disease progression, they will be considered DLT evaluable if they have received at least 7 days of the target dose of blinatumomab.

The occurrence of any of the following toxicities will be considered a DLT, if judged by the investigator to be related to blinatumomab administration:

- grade 5 toxicity
- grade 4 non-hematologic toxicity (non-laboratory)
- grade 4 hematologic toxicity lasting ≥ 7 days (**excluding lymphopenia**)
- grade 4 laboratory abnormalities lasting ≥ 7 days (**excluding lymphopenia**)
- any permanent discontinuation of blinatumomab as described in [Section 6.2.1.3](#)

The stopping rules will use a Bayesian approach to terminate the study if the posterior probability that the DLT rate is greater than 25% is $> 90\%$ ([Section 10.3.1](#)).

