9.1.2 Adverse Events

An adverse event is defined as any untoward medical occurrence in a clinical trial subject. The event does not necessarily have a causal relationship with study treatment. The investigator is responsible for ensuring that any adverse events observed by the investigator or reported by the subject are recorded in the subject's medical record.

The definition of adverse events includes worsening of a pre-existing medical condition. Worsening indicates that the pre-existing medical condition or underlying disease (eg diabetes, migraine headaches, gout) has increased in severity, frequency, and/or duration more than would be expected, and/or has an association with a significantly worse outcome than expected. A pre-existing condition that has not worsened more than anticipated (ie, more than usual fluctuation of disease) during the study or involves an intervention such as elective cosmetic surgery or a medical procedure while on study, is not considered an adverse event.

If the severity of an adverse event changes from the date of onset to the date of resolution, record as a single event with the worst severity on the Event CRF.

For situations when an adverse event or serious adverse event is due to DLBCL, report all known signs and symptoms. Death due to disease progression in the absence of signs and symptoms should be reported as the primary tumor type (eg, DLBCL).

Note: The term "disease progression" should not be used to describe the disease-related event or adverse event.

An adverse device effect is any adverse event related to the use of a medical device. Adverse device effects include adverse events resulting from insufficient or inadequate

instructions for use, adverse events resulting from any malfunction of the device, or adverse events resulting from use error or from intentional misuse of the device.

The investigator's clinical judgment is used to determine whether a subject is to be removed from treatment due to an adverse event. In the event a subject, or subject's legally acceptable representative requests to withdraw from protocol-required therapies or the study due to an adverse event, refer to [Section 8.1](#) for additional instructions on the procedures recommended for safe withdrawal from protocol-required therapies or the study.

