10.3 Planned Analyses

10.3.1 Interim Analyses

Amgen will conduct evaluations of the ongoing DLT rate to assess if the threshold for early trial termination as defined in [Section 6.2.2](#) has been reached. The stopping rules use a Bayesian approach to terminate the study if the posterior probability that the DLT rate is greater than 25% is > 90%. The stopping boundaries assume a prior distribution of (0.50, 1.50) are presented in [Table 7](#) and the operating characteristics with pre-specified batch size of 10 new subjects per batch are presented in [Table 8](#). The

evaluations could occur more frequently if necessary to address emerging safety concerns. The operating characteristics in [Table 8](#) provide the probability of stopping the trial early for given hypothetical true DLT rates, whereas the stopping criteria in [Table 7](#) are based on situations where the empirical evidence would result in a posterior probability of $\geq 90\%$ that the true DLT rate is $\geq 25\%$.

Table 7. Stopping Boundary With Posterior Probability of 90% and DLT Limit of 25%

Number of DLT evaluable subjects (inclusive)	Stop study if observing these many DLTs
10	≥ 5
20	≥ 8
30	Study completes

DLT = dose limiting toxicity

Table 8. Operating Characteristics With Batch Size of 10 Subjects

True DLT rate	Probability of stopping	Average sample size
0.20	5%	30
0.25	14%	28
0.30	27%	26
0.35	44%	24
0.40	62%	21

DLT = dose limiting toxicity

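### Criterion 2 of the DLT Analysis Set can add only subjects without a DLT, and it counts them as DLT-free with no minimum exposure, unlike other removals.

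*Protocol*

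**What the plan says.** Protocol 10.1.2.5 joins four criteria with OR:

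- Criterion 1: "The subject experiences a DLT in the DLT evaluation period; OR"
- Criterion 2: "The subject is removed from treatment for an adverse event/toxicity; OR"
- Criterion 3: removal for a reason other than an adverse event or toxicity, "and the subject has received at least 7 days of the target blinatumomab dose; OR"
- Criterion 4: no DLT, and the evaluation period completed.

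SAP 6.5 repeats the list. The evaluation period is the whole of cycle 1.

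Section 6.2.2 states the exposure condition only for removals that are not for toxicity: "they will be considered DLT evaluable if they have received at least 7 days of the target dose of blinatumomab". It also defines a DLT. A listed toxicity counts only "if judged by the investigator to be related to blinatumomab administration", and the list includes "any permanent discontinuation of blinatumomab as described in" Section 6.2.1.3.

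Removal for an adverse event is not confined to the 6.2.1.3 list. Section 8.3.2 names adverse events and the 6.2.1.3 criteria as separate reasons, and Section 9.1.2 says that the investigator's "clinical judgment is used to determine whether a subject is to be removed from treatment due to an adverse event".

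Section 10.3.1 stops the study when the "posterior probability that the DLT rate is greater than 25% is > 90" per cent. Table 7 counts DLT-evaluable subjects and sets the boundary at 5 or more DLTs in 10, or 8 or more in 20.

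**The concern.** Two removals with equally little exposure are treated differently. A subject who leaves on day 10 for a reason unrelated to safety, before any target dose, is not evaluable. A subject taken off on day 2 at 9 µg/day for an adverse event that is not a DLT is evaluable and counts as DLT-free, although that subject never received 28 or 112 µg/day. Neither document explains the difference.

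The Bayesian boundary is the trial's only quantitative stopping rule, and its looks are small. A subject who adds to the denominator without having been exposed to the full regimen can only lower the posterior probability. The effect therefore has one direction: stopping becomes less likely.

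**Working it through.** **Inputs.** The prior (0.50, 1.50), the 25% limit, the 90% threshold and the batches of 10 come from protocol 10.3.1. The prior's family is not named; I read it as Beta. The share f of evaluable subjects who enter only by criterion 2 is in neither document, so I show 5%, 10% and 20% as assumptions.

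**1. The plan's own figures.** With x DLTs in n subjects, the posterior is Beta(0.5 + x, 1.5 + n − x), and the rule stops if P(rate > 0.25) > 0.90.

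- n = 10: x = 4 gives 0.812 (continue); x = 5 gives 0.935 (stop).
- n = 20: x = 7 gives 0.814 (continue); x = 8 gives 0.913 (stop).

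Table 7 is reproduced. For Table 8, with X the DLTs in the first 10 subjects and Y those in the next 10, both binomial at rate p:

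P(stop) = P(X ≥ 5) + Σ over x = 0 to 4 of P(X = x) · P(Y ≥ 8 − x)

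At p = 0.30 this is 0.1503 + 0.1226 = 0.2729.

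| True rate | P(stop), computed | Table 8 | Mean n, computed | Table 8 |
|---|---|---|---|---|
| 0.20 | 5.2% | 5% | 29.15 | 30 |
| 0.25 | 13.7% | 14% | 27.85 | 28 |
| 0.30 | 27.3% | 27% | 25.77 | 26 |
| 0.35 | 44.5% | 44% | 23.06 | 24 |
| 0.40 | 62.3% | 62% | 20.10 | 21 |

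The stated mean sizes are the computed ones rounded up. The calculation puts every evaluable subject at the true DLT rate, which corresponds to f = 0.

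**2. Whom criterion 2 adds.** Criterion 1 holds all subjects with a DLT in the evaluation period. Someone who enters by criterion 2 but not by criterion 1 therefore has no DLT. From Sections 6.2.2, 8.3.2 and 9.1.2, two groups remain: removals for events judged unrelated, and removals on judgment for events outside 6.2.1.3 and the other DLT items. As an illustration, a grade 3 cytokine release syndrome at 9 µg/day might improve within the permitted time, yet the infusion is not restarted. That case is on neither list.

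**3. Effect on the operating characteristics.** If the rate among the other evaluable subjects is p, the rule sees p(1 − f). Rerunning the same two-look formula gives:

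| f (assumed) | p = 0.30: rate seen | P(stop) | p = 0.40: rate seen | P(stop) |
|---|---|---|---|---|
| 0 | 0.300 | 27.3% | 0.400 | 62.3% |
| 5% | 0.285 | 22.7% | 0.380 | 55.4% |
| 10% | 0.270 | 18.5% | 0.360 | 48.2% |
| 20% | 0.240 | 11.6% | 0.320 | 33.9% |

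**4. How many such subjects matter.** Start one DLT short of the boundary and take criterion-2-only subjects out of the denominator.

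- First look: 4/10 = 0.812, 4/9 = 0.862, 4/8 = 0.906.
- Second look: 7/20 = 0.814, 7/19 = 0.849, 7/18 = 0.881, 7/17 = 0.909.

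It takes two such subjects among the first 10, or three among the first 20, to move the posterior across 90%.

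**The case against.** A reader might infer that removals for toxicity in general dilute the DLT rate, so that a dose subjects cannot tolerate looks safer. The documents do not support this. Section 6.2.2 makes related permanent discontinuations under 6.2.1.3 DLTs at any dose. That list covers grade 4 events, non-resolving or recurrent grade 3 events, a second seizure and the liver criteria. These removals raise the rate.

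Three further objections have force.

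- **Choice of denominator.** The 30% in the working is the rate among the other evaluable subjects. With f = 20% the rate over the whole set is 24%, below the limit, and a low stopping probability is then what the rule should give. A removal for an adverse event is also an observed safety outcome, so counting it can be defended. This stands as a reason to justify the choice. The plan gives no justification, and its own test for other removals points the other way.
- **Off-schedule looks.** 4/8 and 7/17 are not batch looks. If two subjects were left out, the look would wait for two more. At a 30% rate the chance that at least one of them has a DLT and the count reaches 5/10 is 1 − 0.7² = 51%. The contrasts in step 4 show sensitivity, not certain missed stops.
- **DRT review.** Sections 10.3.2 and SAP 7.2 have the DRT evaluate adverse events and DLTs in all subjects, every 10th subject or every 6 months. This softens the risk, but it does not correct the count that enters the boundary.

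**Conclusion.** The point holds in a limited form. By the logic of the criteria, criterion 2 contributes only DLT-free subjects, and it does so without the exposure test applied to other removals. The direction is certain: these subjects can only make stopping less likely. The size cannot be fixed from the documents. It rests on the assumed shares, on the Beta reading of the prior (supported by the reproduction of Table 7), and on looks at exactly 10 and 20.

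A reader might also infer that Tables 7 and 8 are wrong. They are not; both reproduce. Table 8 simply describes a population in which every evaluable subject is at risk at the true DLT rate, and criterion 2 can depart from that. One such subject does not change a result that is one DLT short of the boundary.

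**What to change.** In protocol 10.1.2.5 and SAP 6.5, merge criteria 2 and 3: a subject removed from treatment without a DLT, whatever the reason, is evaluable only if the plan's existing test of 7 days at target dose is met. Extend the matching sentence in 6.2.2 to all removals without a DLT.

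State also that criterion 4 covers only subjects who were not removed from treatment early. It has no exposure condition, and Section 6.2.1.3 keeps subjects who stop for an adverse event in other study procedures. Without this limit they could complete the evaluation period and re-enter.

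At each review, show the DRT the number of adverse-event removals that are not DLTs, and the posterior probability with and without them.

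The cost is a wording change in three places and one extra line in the DRT output; no dosing or treatment rule changes. There are two downsides. The looks at 10 and 20 evaluable subjects come later if such removals are frequent. Early removals would then count only when they are DLTs, which pushes the observed rate up and makes the rule somewhat more conservative. If the sponsor prefers to keep criterion 2, the plan should give the reason and still show the DRT both posteriors.
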